7.6.8 Monocyte oxidative burst

Monocyte oxidative burst is assessed *ex vivo* using the Phagoburst™ kit according to the manufacturers' instructions (Glycotope, Germany). 100µL whole blood is incubated with 2×10^7 *E. coli* for 20 minutes at both 37°C (test condition) and on ice (control condition). 20µL 1,2,3-dihydrorhodamine (1,2,3DHR) is then added for a further 20 minutes at 37°C and the oxidation to rhodamine within CD14⁺ monocytes is measured by flow cytometry.

7.6.9 Changes in plasma bacterial DNA

DNA extraction is performed on 400 μ l of blood using Qiagen (Hilden, Germany) QIAamp DNA Mini kits under aseptic conditions. The quantity of 16S ribosomal bacterial DNA (bDNA) is determined and measured by real-time polymerase chain reaction (qPCR). Primers directed against the V7-V9 variable region of the 16S gene (forward: RW01; 5'->3' sequence AACTGGAGGAAGGTGGGGAT, reverse: DG74.R; 5'->3' sequence AGGAGGTGATCCAACCGCA) are combined with a custom fluorescent probe (6-FAM- TACAAGGCCGGAACGTATTACCG-TAMRA; Life Technologies, Carlsbad, USA) at final concentrations of 0.5 μ M and 0.25 μ M, respectively. This is combined with 10ul of Taqman Gene Expression mix (Applied Biosciences, Foster City, USA), 4ul of extracted DNA and PCR-grade water to give a final reaction volume of 20ul. PCR is performed on a StepOne Plus PCR machine (Applied Biosciences, Foster City, USA) with hot-start activation (2 minutes at 50°C, 10 minutes at 95°C) and 40 reaction cycles (15 seconds at 95°C, 30 seconds at 60°C and 60 seconds at 72°C to collect fluorescence). Serial 10-fold dilutions of *E.coli* DNA (0.08 ng/ μ l to 0.000008 ng/ μ l) and a negative control are run to generate a standard curve.

7.6.10 Changes in transient elastography scores

Fibroscan will be used to obtain elastography scores at baseline, Day 28 and Day 90. Changes in scores from baseline will be compared between the two treatment groups.

7.6.11 Canakinumab sample collection

Blood samples (1 mL) will be collected into SST tubes. The blood sample will be allowed to clot over a minimum of 30 minutes at room temperature prior to harvesting of the serum. The serum will be obtained by centrifugation at approximately 2500 rpm for 10 minutes. Serum samples will be split into 2 aliquots (polypropylene tubes) and then stored (within 30 min of preparation) at -20°C or -70°C (approximately) prior to shipment. Canakinumab is stable in serum samples for 12 months at -20°C or at -70°C. All samples will be given a unique sample number. The actual sample collection date and time will be entered on the PK blood collection page of the CRF. Sampling problems will be commented in the CRFs.

7.6.12 Pharmacodynamic assessments

1. Total IL-1 β assessment: Pharmacodynamic assessments (IL-1 β concentrations) will be assessed in serum as per the Assessment Schedule, pre-dose (trough levels).
2. Pharmacodynamic sample collection and processing: Blood samples (1.5 mL) will be collected into SST tubes. The blood sample will be allowed to clot over a minimum of 30 minutes at room temperature prior to harvesting of the serum. The serum will be obtained by centrifugation at approximately 2500 rpm for 10 minutes. Serum samples will be split into 2 aliquots (polypropylene tubes) and then stored (within 30 min. of preparation) at -20°C or -70°C (approximately) prior to shipment. IL-1 β is stable in serum samples for 12 months at -20°C or -70°C.

7.6.13 Other assessments

1. HIV test: An HIV test will be performed at screening (HIV test conducted within 6 months of screening may be accepted). Patients with a known infection with HIV at screening or randomisation will be excluded from participating in the trial.
2. Pregnancy Test (in females of reproductive age): A pregnancy test will be performed as a serum test at screening and pregnant patients excluded from participation. A urinary pregnancy test will be performed at day 90. If a subject or his partner becomes pregnant whilst taking part in the trial they will be followed up according to Section 9.6.
3. Hepatitis B & C Serology: Serology will be undertaken at screening (Hep B/C result performed within 6 months of screening may be accepted) and evidence of chronic viral hepatitis (B or C) will exclude the patient from participation.
4. Genetic sequencing: Genetic sequencing will be carried out at screening.
5. Alcohol consumption: Details on alcohol consumption will be collected at screening, day 28, day 42 and day 90.
6. Calorie and protein intake: Details on calorie and protein intake will be collected at all visits apart from screening.
7. Liver ultrasound (USS): A liver ultrasound will take place at screening only and is part of Standard of Care for the patients.
8. Stool and saliva samples will be collected at baseline and days 14, 28 and 90.
9. Exploratory BM serum to be collected (2 x 500ul) at baseline and all subsequent visits.

8 Statistical Considerations

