3.6. Treatment

Patients will be included and randomized and treated before histology result is available. If the histology is negative then patient will be withdrawn.

A single dose of 3 mg/kg Canakinumab or identical placebo will be administered intravenously at baseline (Day 1). Canakinumab will be made up by dilution in 100 ml 5% Dextrose by an unblinded research personnel at each site. The drug or placebo (5% Dextrose alone) will be labelled by the designated unblinded team member.

Patients with moderate to severe ascites should undergo large volume paracentesis prior to administration of Canakinumab.

Patients with AST >2 x ULN on Day 28 will receive a second dose of 3 mg/kg study drug administered i.v. on Day 28:

- Patients who received placebo on baseline will receive placebo.
- Patients who received canakinumab on baseline will receive canakinumab.

The second dose of study drug (or placebo) should not be administered if the patient experienced an incident of infection during the prior 28 days, MELD >27 or in cases where the PI is concerned about the patient's condition deteriorating.

Randomisation will be via the trial InForm database which will enable the unblinded research team to ensure the right dosing and drug preparation in respect of the AST assessment on D28.

4. Patient population

The trial will be conducted in patients with severe alcoholic hepatitis (mDF* ≥ 32 and MELD ≤ 27) with treatment initiated during an index hospital admission with the condition.

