| Acute kidney injury assessment [§] | X | X | X | X | X | X | X | X | X | |
| EDTA sample for DNA (16S) | X | X | X | X | X | X | | | X | |
| PBMC sample [~] | | X | X | X | | X | | | X | |
| Infection/ Sepsis/ SIRS screen | X | X | X | X | X | X | X | X | X | X |
| USS Liver assessment [§] | X | | | | | | | | | |
| Fibroscan measurement [§] | | X | | | | X | | | X | |
| Gene expression sample | | X | | | | X | | | | |
| Liver biopsy (incl. HVPG measurement [*]) [§] | | | X | | | X | | | | |
| Adverse events | | X | X | X | X | X | X | X | X | |
| PK/PD samples in blood and ascites fluid # | | X | X | X | X | X | X | | X | X |
| Biomarker serum | | X | X | X | X | X | X | X | X | |
| Stool & saliva sample | | X | | X | | X | | | X | |

Footnotes to Schedule of Assessments

| | | |
|---------------|--|---|
| ¹ | Day 42 visit | Required for patients who received second dose study drug at Day 28 |
| ² | Day 28 visit | A Day 28 assessment/follow up treatment/biopsy can be performed between Day 25 and Day 35 |
| ³ | Day 90 visit | A Day 90 assessment can be performed 14 days either side of the target date |
| ⁴ | Day 7, 14, 21, 42 visits | For Day 7, 14, 21 and 42 assessments a tolerance of 48 hrs in time window either way is accepted |
| ⁵ | Screening pregnancy test | Needs to be performed as serum test |
| ⁶ | Screening and baseline samples | If baseline visit is performed within 72 hours since screening, then screening samples which repeat at baseline may be accepted on baseline date. |
| ⁷ | Screening and Baseline visit | The maximum time between screening and date baseline is 7 days |
| ⁸ | Baseline liver biopsy acceptance window | The maximum timeframe for a baseline biopsy to be accepted into the trial is 7 days before baseline visit (day of Randomisation and study drug administration). |
| ⁹ | Baseline visit | Allowance of -1 day is accepted to allow for blood results to come through for re-confirmation of eligibility before randomisation and IMP/Placebo administration. Baseline date of visit should always be the date of randomisation and IMP administration. |

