| ¹⁰ | Discharge | Patients who are discharged during the follow-up period are not required to attend further weekly visits other than on Day 28 (when the potential second IMP dose and second biopsy is taking place), Day 42 (if second Imp dose was administered) and Day 90, which is the end of study visit. Patients due to be discharged will have the samples collected on discharge, as specified in the schedule of assessments below |
| ¹¹ | Baseline; Day 28 | Sample collection is pre-IMP administration. |
| # | Pharmacokinetic and pharmacodynamics samples - blood and ascitic fluid | In case of ascites, ascites fluid sample needs to be collected only once, at the time when patient is having ascites tapped for clinical purposes. |
| * | TJ liver biopsy | HVPG measurement should be collected in all TJ liver biopsies. |
| ^ | Virology screening | Results within 6 months of screening may be accepted without the need to repeat |
| + | Screening and Day 90 pregnancy tests | Pregnancy test required only for females of reproductive age only |
| ~ | PMBC | PBMC, which are to be sent to a central lab immediately after collection, should not be collected on Friday or Saturday in order to avoid loss of sample due to a weekend staff cover at the central laboratory. When PMBCs are posted out, an email notification must be sent, as per study Lab Manual. |
| % | Haematology & Biochemistry | ± 1 day of screening date |
| \$ | Overt GI haemorrhage assessment, AKI assessment; Fibroscan, USS | From day of admission onwards |

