9.6 Pregnancy

If a subject or his partner becomes pregnant whilst taking part in the trial or during a stage where the foetus could have been exposed to an IMP, the Investigator must ensure that the subject and the subject's healthcare professional are aware that follow-up information is required on the outcome of the pregnancy. If the subject leaves the area, their new healthcare professional should also be informed. Each pregnancy occurring while the patient is on study treatment must be reported to ICTU within 24 hours of learning of its occurrence. Any SAE experienced during the pregnancy and unrelated to the pregnancy must be reported on a SAE form. The pregnancy should be followed up to determine outcome, including spontaneous or voluntary termination, details of the birth, and the presence or absence of any birth defects, congenital abnormalities, or maternal and/or newborn complications. Pregnancy follow-up should be recorded on the same form and should include an assessment of the possible relationship to the investigational treatment.

Study treatment for pregnant participants must be discontinued immediately.

Contraception

The following methods of contraception are accepted:

- (i) Total abstinence (when this is in line with the preferred and usual lifestyle of the subject). Periodic abstinence (e.g., calendar, ovulation, symptothermal, post-ovulation methods) and withdrawal are not acceptable methods of contraception.
- (ii) Female sterilization (have had surgical bilateral oophorectomy with or without hysterectomy) or tubal ligation at least six weeks before taking study treatment. In case of oophorectomy alone, only when the reproductive status of the woman has been confirmed by follow up hormone level assessment.
- (iii) Male sterilization (at least 6 months prior to screening). For female subjects on the study, the vasectomized male partner should be the sole partner for that subject.
- (iv) Barrier methods of contraception: Condom or Occlusive cap (diaphragm or cervical/vault caps) with spermicidal foam/gel/film/cream/ vaginal suppository.

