10.2 Patients not lost

Patients that fall into one or more of the following categories, which are indications for treatment discontinuation, are not considered as withdrawn or lost from the study. They should continue to attend all follow-up study assessments as per protocol, unless they subsequently fall into one of the categories listed in Section 10.1;

- Patients who ask to stop study treatment
- Pregnancy
- Steroid psychosis or persisting psychotic symptoms for more than 7 days, that cannot be explained by alcohol withdrawal
- Any event which in the judgement of the PI makes further study treatment inadvisable
- SAE requiring discontinuation of treatment.

Stopping treatment or having a prolonged/numerous treatment gaps, for whatever reason, does not mean the patients are withdrawn or lost from the study, they should still continue to attend all follow-up assessments. If the screening biopsy histology is negative then the patient will be discontinued from the study, will not undergo any further treatment or the second biopsy but will be followed-up for safety assessment for 28 days, as per assessment schedule.

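### No pregnancy test is scheduled between the Day 1 dose and the conditional second dose at Day 28

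*Combined protocol and SAP*

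**What the plan says.** **Testing.** Section 7.6.13 requires a serum test at screening, excludes women found pregnant, and adds: "A urinary pregnancy test will be performed at day 90". Sections 7.1 and 7.4 list the same two tests. In Table 1 (section 7.5) the pregnancy row is marked only under Screening and Day 90, and its footnote is labelled for those two visits. Neither the baseline list (7.2) nor the list for Days 7, 14, 21, 28 and 42 (7.3) contains a pregnancy test.

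**Second dose.** Section 3.6 states: "Patients with AST >2 x ULN on Day 28 will receive a second dose of 3 mg/kg study drug". It withholds that dose for infection in the preceding 28 days, MELD above 27, or the principal investigator's concern that the patient is deteriorating. Neither pregnancy nor a negative test appears there. Footnote 2 of Table 1 sets the window: "A Day 28 assessment/follow up treatment/biopsy can be performed between Day 25 and Day 35".

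**Pregnancy during the trial.** Section 9.6: "Study treatment for pregnant participants must be discontinued immediately". Section 10.2 includes pregnancy among the events "which are indications for treatment discontinuation, are not considered as withdrawn or lost from the study". Women of child-bearing potential must use effective contraception (4.4.1), maintained for the whole study (9.6).

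**Contact before Day 28.** Footnote 10 of Table 1: "Patients who are discharged during the follow-up period are not required to attend further weekly visits other than on Day 28"; the Day 42 visit (if re-dosed) and the Day 90 visit also remain.

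**The concern.** A stopping rule works only if the condition that triggers it can be found before the treatment it is meant to stop. Apart from the Day 1 infusion, the only study treatment is the conditional Day 28 infusion. The screening test protects both doses against pregnancy present at entry, but the one later test comes after dosing has ended. A woman who became pregnant after screening and did not know it, whose AST met the threshold and who had none of the section 3.6 bars, would be re-dosed under the schedule as written.

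Recognition by symptoms may be unreliable in this population. Appendix 2 lists amenorrhea, menstrual irregularity and vomiting among the protocol-exempt events, so a missed period could be put down to the liver disease. Patients discharged early may also have little trial contact until Day 28.

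What is at stake is avoidable fetal exposure to a second dose of canakinumab. The efficacy analysis is not affected.

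**Working it through.** The plan states no figure on this point, so there is nothing to reproduce. The check has two parts: a count of scheduled tests before re-dosing, and the intervals that the visit windows allow.

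**Count.** Sections 7.1 to 7.4, 7.6.13 and Table 1 agree. Scheduled pregnancy tests after screening and before the second dose: 0.

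**Inputs**

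| Input | Value | Source |
|---|---|---|
| First dose (baseline) | Day 1 | 3.6 |
| Screening to baseline | 0 to 7 days: "The maximum time between screening and date baseline is 7 days" | Table 1, footnote 7 |
| Second dose | Day 25 to 35, nominal Day 28 | 3.6; Table 1, footnote 2 |
| Final test | Day 90 ± 14 = Day 76 to 104 | Table 1, footnote 3 |

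**Age of the last scheduled test at the second dose** = (dose day − 1) + (days from screening to baseline)

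- Minimum: (25 − 1) + 0 = 24 days
- Maximum: (35 − 1) + 7 = 41 days
- Dose exactly on Day 28: (28 − 1) + 0 to 7 = 27 to 34 days

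**Second dose to the next scheduled test** = (test day − dose day)

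- Minimum: 76 − 35 = 41 days
- Maximum: 104 − 25 = 79 days
- Dose on Day 28: 76 − 28 = 48 to 104 − 28 = 76 days; with both visits on their nominal days, 90 − 28 = 62 days

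**Interval between the two scheduled tests** = (final test day − 1) + (days from screening to baseline)

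- Minimum: (76 − 1) + 0 = 75 days
- Maximum: (104 − 1) + 7 = 110 days

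If baseline were counted as Day 0, the intervals measured from screening would each lengthen by one day (24 to 41 becomes 25 to 42). Those measured from the second dose would not change.

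**Can the other provisions find the pregnancy?**

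- The section 3.6 bars concern infection, MELD and deterioration. An uncomplicated early pregnancy meets none of them.
- Sections 9.6 and 10.2 act once a pregnancy is known. They do not find one.
- Contraception lowers the chance of pregnancy but does not detect it. The protocol does not rely on it alone, since it still tests at Day 90.
- The Day 28 visit includes a physical examination, a medication review and adverse event questioning. These may prompt suspicion, but none is a pregnancy test.

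**The case against.** The strongest reply is that this is a deliberate and consistent choice. Every section agrees on two tests, and sections 9.6 and 10.2 say what to do about a known pregnancy without promising a test before each dose. Several safeguards already apply: the serum test and exclusion at entry, mandatory contraception, stopping on known pregnancy, the investigator's discretion to withhold treatment, and a clinical visit at which the second dose is given. The residual case needs failed contraception, an unrecognised pregnancy, AST above the threshold, no section 3.6 bar and allocation to active drug, all within a trial of 52 patients. The documents contain no reproductive-toxicity data, and a woman who conceived after screening may already have been exposed through the Day 1 dose. Any amendment also needs ethics committee and MHRA approval and notification of the HRA and all sites (12.4 to 12.6), in up to 18 centres (1.4).

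Much of this stands. The event would be rare, the added harm of a second dose cannot be sized from the documents, the intervals describe the calendar rather than risk, and the administrative cost exceeds a table edit. The point about thin contact is also limited, because the second dose can be given only at an attended visit.

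None of it supplies detection before re-dosing. A consistent schedule can still leave a stopping rule without the information it needs, and the protocol itself holds that treatment in pregnancy must stop.

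**Conclusion.** The concern holds. No scheduled test can identify a pregnancy that arises after screening before the second dose is given. At that dose the last test is 24 to 41 days old, and the next follows 41 to 79 days later.

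The conclusion is limited in three ways:

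- It covers only pregnancies arising after screening and unrecognised by Day 28. A pregnancy known by any route already bars the dose.
- No number of women or pregnancies can be given, because the documents report no sex mix, share of child-bearing potential or re-dosing rate. That few would be affected is an assumption, and nothing above depends on it. With 1:1 randomisation, about half of those re-dosed would be expected to receive dextrose alone.
- The primary endpoint, sample size and analysis are unaffected.

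The change is worth making because the exposure is one the protocol already says must not continue, and a simple test at an existing visit would guard against it.

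**What to change.** In Table 1 and sections 7.3 and 7.6.13, add a urine pregnancy test at the Day 28 visit for women of reproductive age being considered for the second dose, and require a negative result before infusion. A cross-reference in section 3.6 to 9.6 and 10.2 would be useful but is optional.

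The test fits the visit as designed. Urine is already collected at Day 28 for ethyl glucuronide (7.3), and footnote 11 of Table 1 says of baseline and Day 28: "Sample collection is pre-IMP administration". Dosing already waits on that day's AST. A positive strip could be confirmed by serum test within the Day 25 to 35 window, provided the visit falls before Day 35. Done before the Day 28 biopsy, which uses X-ray guidance (7.6.5), the result would inform that procedure too.

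The cost is one extra mark in Table 1, one sentence in each of 7.3 and 7.6.13, probably an eCRF field, and one test strip per eligible woman. The amendment needs the usual approvals and site notification, so it is best combined with the next planned one. Sites should confirm that the ethyl glucuronide sample can be tested at the bedside, since the documents do not say how it is handled; if it cannot, a separate urine sample is needed.

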8.1 Power calculation

It is estimated that improvement of histological alcoholic steatohepatitis will occur in 40% of patients treated with placebo and 80% of patients treated with Canakinumab. A trial with 80% power to detect a difference at the $P < 0.05$ threshold would require 23 patients in each arm, 46 in total. Assuming a drop-out rate of 10%, we will recruit 52 patients in total (26 patients per group). Patients will be included and randomized and treated before histology result is available. If the histology is negative, then patient will be withdrawn and another patient recruited. Additionally, to meet the study power we will continue recruitment until we have paired biopsies in 48 patients.

8.2 Statistical Analysis Plan

A statistical analysis plan will be drafted prior to the first data extraction.

The primary analysis will estimate the difference between the groups in proportion of patients with improvement of the disease using a chi square test. Logistic regression, adjusted for histology baseline values, will investigate the relationship between disease histological improvement and other independent variables including the baseline severity (MELD score), age and gender. All statistical tests will be two-tailed with a 5% significance level. Further details of the planned analysis of the

secondary outcomes and methods for dealing with missing data will be given in the Statistical Analysis Plan.

There is no planned interim or subgroup analyses. Any deviations from the statistical analysis plan will be dealt with in accordance with Imperial Clinical Trial Unit's statistical Standard Operating Procedures.

9. Assessment of Safety

9.1 Definitions of Adverse Events

The Medicines for Human Use (Clinical Trials) Regulations 2004 (UK), as amended, provides the following definitions relating to adverse events in trials with an investigational medicinal product:

Adverse Event (AE):

Any untoward medical occurrence in a subject to whom a medicinal product has been administered including occurrences which are not necessarily caused by or related to that product.

Adverse Reaction (AR):

Any untoward and unintended response in a subject to an investigational medicinal product, which is related to any dose administered to that subject. All AEs judged by either the reporting investigator or the sponsor as having reasonable causal relationship to a medicinal product qualify as adverse reactions.

Serious Adverse Event (SAE):

Any adverse event that:

- results in death;
- is life-threatening;
- requires hospitalisation or prolongation of existing hospitalisation;
- results in persistent or significant disability or incapacity, or
- consists of a congenital anomaly or birth defect
- Is medically significant

Note: The term 'life-threatening' in the definition of 'serious' refers to an event in which the patient was at risk of death at the time of the event; it does not refer to an event which hypothetically might have caused death if it were more severe.

Hospitalisation means any unexpected admission to a hospital department. It does not usually apply to scheduled admissions that were planned before study inclusion or visits to casualty (without admission).

The term 'medically significant' is defined as an event that jeopardises the patient or may require medical or surgical intervention.

Serious Adverse Reaction (SAR)

A SAR is defined as a SAE that is judged to be related to any dose of study drug administered to the subject or withdrawn from the subject.

Suspected Unexpected Serious Adverse Reaction (SUSAR)

Any SAR that is NOT consistent with the applicable product information as set out in the Investigator Brochure (IB) or Summary of Product Characteristics (SmPC) i.e. is unexpected as per Appendix 2.

